9.3 Interim Analysis

Interim analysis will be performed after 33% of the planned sample size of randomized patients complete 12-month care. To preserve the overall type I error rate at < 0.05 , the Lan-DeMets spending function will be used to allocate nominal alpha-levels at the interim and final analyses. The efficacy stopping boundaries for the primary efficacy endpoint at the interim and final analyses are $p < 0.026$ and $p < 0.474$, respectively.

An interim analysis for the non-randomized cohort will be performed after 10 patients have been enrolled on the STAND clinic for a minimum of 6 months. If the percentage of completed STAND visits is less than 60%, the study schedule will be altered to ensure higher rates of patient adherence to the clinic schedule.

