9.2 Determination of Sample Size and Study Power

The sample size estimate is based upon the primary endpoint of the study, the mean percent change in percentage body fat from baseline to 12 months. Based on prior prospective longitudinal studies, it is estimated that men receiving ADT and standard-of-care physician counseling regarding expected toxicities will experience a mean 12% (sd = 17%) increase in percentage body fat after 12 months of ADT [13]. If men participating in the STAND clinic, with individualized exercise/nutrition counseling and longitudinal assessment, have, on average, no increase in percentage body fat mass after 12 months of hormone therapy, this would warrant further evaluation of a multi-disciplinary clinic in a larger randomized clinical trial with long-term endpoints of interest, including incidence of diabetes and potentially cardiovascular disease. An enrollment target of 32 evaluable patients per arm will provide power of 80% to detect an effect size of 0.71 in the difference in mean percent change from baseline to 12 months in percentage body fat mass between the two arms, using a two-sample t test and a two-tailed level of significance = 0.05. The total planned accrual is 40 patients per arm accounting for an inevaluable rate of 20%.

A sample size of 20 patients is chosen for the non-randomized chemohormonal cohort to establish the feasibility of a multi-disciplinary clinic in this patient population. The primary endpoint for this pilot cohort is the percentage of completed STAND clinic visits, with a target goal of 80%. A sample size of 20 patients (13 visits per patient; 260 visits in total) provides 17.5% precision to determine the percentage of completed visits at 95% confidence.

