9.8 Methods for Analysis

Generally, frequency distributions, means, and standard deviations will be used to describe subject demographics and baseline characteristics. Univariate analysis among variables will be assessed using the two-sample t-test, Wilcoxon-rank-sum test, Chi-square test, as appropriate. Statistical significance will be declared based on alpha level of 0.05. For the endpoints with missing less than 25% of values, multivariate imputation using fully conditional specification (R MICE package) will be implemented. For endpoints missing more than 25% of values, the endpoint will be excluded from the final analysis.

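### The efficacy boundaries printed in section 9.3 (0.026 interim, 0.474 final) cannot hold the overall type I error below 0.05; each has probably lost a zero

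*Combined protocol and SAP*

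**What the plan says.** All of this comes from the combined protocol and SAP.

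- **Section 9.3, timing:** "Interim analysis will be performed after 33% of the planned sample size of randomized patients complete 12-month care". There is one interim and one final analysis.
- **Section 9.3, purpose:** the stated aim is "To preserve the overall type I error rate at < 0.05".
- **Section 9.3, method:** as the means to that aim, the section says that "the Lan-DeMets spending function will be used to allocate nominal alpha-levels at the interim and final analyses". The form of the function (O'Brien-Fleming type, Pocock type or another) is not named.
- **Section 9.3, boundaries for the primary efficacy endpoint:** "at the interim and final analyses are $p < 0.026$ and $p < 0.474$, respectively".
- **Section 9.2, design test:** "using a two-sample t test and a two-tailed level of significance = 0.05", with 32 evaluable patients per arm, a 12-point target difference, SD 17, and 40 per arm enrolled.
- **Section 9.8, general rule:** "Statistical significance will be declared based on alpha level of 0.05". It does not refer back to the boundaries in 9.3.

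No other section restates or corrects the two boundary values.

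**The concern.** The paragraph states an aim and then gives numbers that cannot meet it. A procedure that rejects whenever the final p-value is below 0.474 has an overall error of at least 0.474, whatever happens at the interim and whatever spending function is used.

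These two numbers are the efficacy stopping rule and the success threshold for the primary endpoint. The final figure is implausible enough that most readers would notice it. The interim figure is the more dangerous one. A level of 0.026 looks like an ordinary interim boundary, so it could be applied as printed, on about 26 men, with the final figure silently read as 0.0474 or 0.05. That partial repair still breaks the 0.05 limit. If 0.0026 was intended, the interim boundary is ten times too loose.

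**Working it through.** **Inputs.** Overall two-sided alpha 0.05 (9.2, 9.3); interim at t = 0.33 and boundaries 0.026 and 0.474 (9.3); 32 evaluable per arm, difference 12, SD 17 (9.2); 80 randomized (9.4).

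**The sample size in 9.2 reproduces.** n per arm = 2(1.96 + 0.84)²/0.71² = 31.1, so 32. The t-test power at 32 per arm is 79.8%, and 32/(1 − 0.20) = 40. The problem is confined to the boundaries.

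**Overall error.** Let Z1 and Z2 be the interim and final statistics, bivariate normal under the null with correlation √t = √0.33 = 0.574. Then

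overall error = 1 − P(|Z1| < z1 and |Z2| < z2),

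where z1 and z2 are the two-sided critical values. For the printed pair, z1 = 2.226 and z2 = 0.716.

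| Interim p | Final p | Overall two-sided error | In one direction |
|---|---|---|---|
| 0.026 | 0.474 (as printed) | 0.479 | 0.239 |
| 0.0026 | 0.474 | 0.474 | 0.237 |
| 0.026 | 0.0474 | 0.066 | 0.033 |
| 0.026 | 0.05 | 0.069 | 0.034 |
| 0.0026 | 0.0474 | 0.0488 | 0.024 |
| 0.0026 | 0.0486 | 0.0500 | 0.025 |

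Simulated two-sample t tests (200,000 trials, at 11 then 32 per arm and at 13 then 40 per arm) give 0.479 to 0.480 for the printed pair, 0.067 for 0.026/0.0474 and 0.049 for 0.0026/0.0474.

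**Final level that would hold 0.05.** Given 0.026 at the interim, 0.029. Given 0.0026, 0.0486.

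**Where the printed figures may come from.** At t = 0.33:

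- Hwang-Shih-DeCani, γ = −4: 0.05(1 − e^{4t})/(1 − e^{4}) = 0.00256 spent, leaving 0.05 − 0.00256 = 0.04744. These are the printed digits with a zero restored in each. The nominal final level is 0.0486.
- O'Brien-Fleming type: 0.0002 to 0.0007 (depending on whether the function is applied to each side or to the whole 0.05), then about 0.050.
- Pocock type: 0.05 ln(1 + (e − 1)t) = 0.0225, then 0.0326.

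Also, 0.0026 + 0.0474 = 0.0500 exactly. On this reading 0.0474 is the alpha left after the interim. Used as a nominal level it is slightly conservative.

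**Sensitivity to the information fraction.** 33% of 80 is about 26 completers. Measured against the 64 evaluable patients planned for analysis, 26/64 = 0.41. There the printed pair gives 0.477 and 0.026/0.0474 gives 0.065.

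**What the final threshold means in points.** The standard error is 17√(2/32) = 4.25. With 62 degrees of freedom, p < 0.474 is met by an observed difference of 0.720 × 4.25 = 3.1 points; p < 0.0486 needs 2.012 × 4.25 = 8.55 points. The target is 12.

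**The case against.** The contradiction is hard to dispute, but four points narrow what should be made of it.

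- **The lost-zero explanation is not proven.** The γ = −4 match was found by trying several functions, and a power-family function with exponent about 2.67 also spends 0.0026 at t = 0.33. There is a rival reading too: Pocock-type spending gives 0.0265 at t = 26/64, so 0.026 might be right and only the final figure wrong. But that reading needs a final level near 0.030, which matches neither 0.474 nor 0.0474. The lost-zero reading explains both figures and their sum, so it is the better inference, though still an inference.
- **Nobody would declare success at p = 0.47.** This is fair. Sections 9.2 and 9.8 both state 0.05, so the realistic exposure is 0.066 to 0.069 through the interim figure, not 0.479. In a single-centre phase 2 trial meant to justify a larger one, that limits the harm. It does not make a wrong stopping boundary acceptable, because the plan itself chose strict control.
- **The 0.05 in 9.8 may be only a general default.** Section 9.3 can be read as the specific rule for the primary endpoint, and 0.0026 followed by 0.05 gives only 0.0514. The cross-reference is therefore a small matter if 0.0026 was intended.
- **Moving from 0.0474 to 0.0486 is optional.** 0.0026/0.0474 already satisfies the stated limit.

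A digit lost when the file was converted cannot be excluded from the text alone, although losing the same zero twice is unlikely. Checking the source file settles that.

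**Conclusion.** The concern holds. As printed, the boundaries give an overall two-sided type I error of about 0.48 (about 0.24 in favour of the STAND clinic) against a stated limit of 0.05. Repairing only the final figure leaves it at 0.066. The first result needs no assumption about the spending function, since 0.474 alone exceeds the limit. The second rests on the usual joint normality with correlation √t and changes little between t = 0.33 and t = 0.41.

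That the intended pair was 0.0026 and 0.0474 is probable but not established, because the plan names no form for the function. This must be fixed before interim data are examined.

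**What to change.** 1. Check the digits against the source file and retrieve the original boundary calculation.
2. Name the spending function in 9.3, with its parameter if it has one.
3. Replace both figures with nominal two-sided boundaries from that function, to be recomputed at the actual information fraction.
4. State the denominator for that fraction. The interim trigger is about 26 of 80 randomized, while the planned maximum for analysis is 64 evaluable.
5. In 9.8 and 9.8.1, say that the primary endpoint is tested at the final level from 9.3 and not at the general 0.05.

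Candidate pairs (interim / final):

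| Function | t = 0.33 | t = 26/64 = 0.41 |
|---|---|---|
| Hwang-Shih-DeCani, γ = −4 | 0.0026 / 0.0486 (0.0474 if the remaining alpha is used) | 0.0038 / 0.0482 |
| O'Brien-Fleming type | 0.0002–0.0007 / 0.050 | 0.0009–0.0021 / 0.049–0.050 |
| Pocock type | 0.0225 / 0.0326 | 0.0265 / 0.0302 |

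**Cost.** This is a short correction in 9.3 and a cross-reference in 9.8. With 32 per arm the drift is 12/4.25 = 2.82, and power by normal approximation at t = 0.33 is 80.6% for a single test at 0.05, 80.4% for 0.0026/0.0486, 80.6% for O'Brien-Fleming type and 76.7% for Pocock type. Only the Pocock-type choice would have a noticeable effect on power.

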9.4 Accrual

A total of 80 patients will be enrolled in the randomized patient cohort at the University of California San Francisco. Study accrual is anticipated to be approximately 2 patients per month, leading to total study accrual duration of 40 months. Anticipated time from last patient enrolled to primary study completion and analysis of primary and secondary endpoints equals approximately 12 months, leading to an estimated primary study duration of 52 months. A total of 20 patients will be enrolled in the non-randomized chemohormonal cohort, at an estimated frequency of 0.8 patients/month, leading to an estimated accrual period of 24 months.

9.5 Analysis Populations

The primary analysis for the randomized cohort will include all patients who have a body fat % measurement at baseline and at month 12 on study (± 2 weeks). If a patient comes off study prior to obtaining the end of month 12 body fat % measurement, they will not be included in the primary study analysis.

All patients enrolled in the chemohormonal non-randomized cohort who complete C1D1 visit will be included in the analysis of the primary endpoint, the percentage of completed visits in the STAND clinic.

9.6 Demographics and Baseline Characteristics

Demographic variables will include age, race, and ethnicity. Baseline characteristics will include the following:

- Height, weight, body mass index, waist circumference, percentage body fat
- Assessment of co-morbidities including diabetes and heart disease (Appendix 3)
- Date of prostate cancer diagnosis
- Gleason grade and PSA at the time of diagnosis
- Type and date of prior local therapy (if any)
- Date of ADT initiation and indication (adjuvant, biochemical relapse, or metastatic disease)
- Baseline PSA at the start of ADT
- Concurrent use of anti-androgen
- Metastatic status at time of study entry (none, bone only, soft tissue, any visceral)

9.7 Study Endpoints

9.7.1 Primary Endpoint

Randomized cohort: Mean percent change from baseline to 12 months in percentage body fat mass as measured by bioelectrical impedance analyzer.

Non-randomized cohort: Percentage of completed STAND clinic visits.

9.7.2 Secondary Endpoints

Mean percent change from baseline to 12 months and patterns of change from baseline with respect to the following:

Metabolic Impact on Diabetes and Cardiovascular Disease Risk Factors:

- Fasting blood glucose
- Fasting plasma insulin level
- Insulin resistance as calculated by HOMA-IR
- Hemoglobin A1c
- Fasting lipids (total cholesterol, LDL, HDL, triglycerides)
- Waist circumference
- Body weight/body mass index
- Exercise patterns as measured by validated questionnaire and pedometer assessment
- Blood pressure

Bone Health:

- Bone density at the lumbar spine, femoral neck, and total hip as assessed by DXA scan among patients without bone metastases at the time of study entry
- Serum 25-(OH) vitamin D levels

Quality of Life/Psychosocial Impact:

- Depression as measured by PHQ-9
- Cognitive function as measured by Attentional Functional Index
- Overall quality of life as measured by SF-12
- Fatigue as measured by the Lee Fatigue Scale
- Erectile and urinary function as measured by EPIC-26
- Hot flash severity as measured by Hot Flash Related Daily Interference Scale

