2.2.2 Secondary Objectives

To compare the mean percent change from baseline to 12 months and patterns of change over time during participation in the STAND clinic vs. usual standard of care with respect to:

Metabolic Impact on Diabetes and Cardiovascular Risk Factors:

- Fasting blood glucose
- Fasting plasma insulin level
- Insulin resistance as calculated by HOMA-IR
- Hemoglobin A1c
- Fasting lipids (total cholesterol, LDL, HDL, triglycerides)
- Waist circumference
- Body weight/body mass index
- Exercise patterns as measured by validated questionnaire and ambulatory accelerometer assessment (see Appendices 2 and 5 respectively)
- Blood pressure

Bone Health:

- Bone density as assessed by DXA scan
- 25-(OH) vitamin D serum levels

Quality of Life/Psychosocial Impact:

- Depression as measured by PHQ-9
- Cognitive function as measured by the Attentional Functional Index
- Overall quality of life as measured by SF-12
- Fatigue as measured by the Lee Fatigue Scale
- Erectile and urinary function as measured by EPIC-26
- Hot flash severity as measured by Hot Flash Related Daily Interference Scale

Among men randomized to receive usual standard of care that cross-over to participate in the STAND clinic after month 12 of the study:

To measure the mean change from baseline at start of participation in the STAND clinic after 12 months of participation in:

- Metabolic parameters including percentage body fat, fasting insulin/glucose, HOMA-IR, body weight/body mass index, waist circumference
- Bone health
- Quality of life
- Patient satisfaction

Among men in the non-randomized pilot cohort:

- To determine the mean change from baseline to 12 months during STAND clinic participation in the primary and secondary metabolic and quality of life parameters listed above.

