9.8.1 Analytic Plan for the Primary Objective

Two-sample t-test will be used to compare the mean percent change from baseline in percentage body fat after 12 months of study participation. The changes in percentage body fat across the

different time points will be evaluated using repeated measures analysis of covariance. To further characterize the patterns over the time and investigate the effect of treatment arm assignment, a linear mixed model will be applied with adjusting for stratification factors and covariates including Charlson co-morbidity index score, age, and baseline depression score as measured by PHQ-9. Patients who do not have a baseline or end-of-month 12 percentage body fat measurement, or those that start medications known to affect body fat/body weight during the course of the 12-month study, including metformin, insulin, corticosteroids, mirtazapine, or megestrol, will be excluded from the primary endpoint analysis. In an exploratory analysis, these patients will be retained to assess the impact of STAND clinic participation on changes in percentage body fat over time both before and after initiation of medical management.

For the non-randomized chemohormonal cohort, the point estimate and 95% confidence interval of the percentage of completed STAND clinic visits will be reported.

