9.8.2 Analytic Plan for the Secondary Objectives

Two-sample t test will be used to compare the mean change from baseline to 12 months for the secondary endpoints which hold the normality assumption. For endpoints that do not hold the normality assumption, as well as for ordinal level of measurements, Wilcoxon-rank-sum test will be used. To evaluate the changes in secondary endpoints across the different time points, repeated measures analysis of covariance will be used for continuous endpoints (appropriate transformation will be applied if normality assumption doesn't hold), while repeated measures generalized estimation equation with a cumulative logic categorical will be applied for the ordinal level of measurements. Generalized linear mixed models with adjustment for stratification factors and possible covariates will be applied to further characterize the patterns over the time and investigate the effect of the care type with appropriate link function. Results will be displayed in a graphical fashion. Patients who start medications known to affect endpoint being analyzed (e.g. statins for the lipid panel measurement) will be excluded from the main statistical analysis. In a sensitivity analysis these patients will be retained to assess impact of STAND clinic participation on study outcomes. No adjustment for multiple comparisons will be made for the analysis of the secondary, exploratory objectives.

For patients who cross-over from standard-of-care to participate in the STAND clinic, the mean change from month 12 to month 24 after twelve months of participation in the STAND clinic with respect to the study endpoints will be descriptively reported.

During the follow-up phase of the study, the mean change from completion of STAND clinic participation to 12 months after completion with respect to study endpoints will be descriptively reported.

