9.8.3 Analytic Plan for the Correlative Objectives

The relationship between each pre-selected SNP genotype and the percent change from baseline to 12 months on-study in percentage body fat, fasting plasma glucose, body mass index, waist circumference, and fasting insulin among men undergoing ADT will each be tested using a two-sample t test or Wilcoxon-rank-sum test as appropriate when the SNPs are in dominant or recessive fashion. When SNPs are in the additive model, for each SNP, a generalized linear model with an appropriate link will be used considering each baseline-12 month change as the response variable and SNP genotype (coded as 0, 1, and 2 for zero, one and two copies of minor allele) as the predictor. Analysis will be extended to adjust for possible risk factors by fitting multivariate generalized linear models for each baseline-12 month change and each SNP. Multiple testing adjustments will be done for each baseline-12 month change across all SNPs by controlling for false discovery rate.

The mean percent change from baseline in trabecular bone microarchitecture parameters including trabecular bone number and trabecular bone volume assessed by high resolution quantitative peripheral CT will be descriptively reported for the entire study population. In an exploratory fashion, the mean percent change between those randomized to the STAND versus usual care treatment arms will be compared using Mann-Whitney test.

The distribution of the 2D:4D finger length ratio will be determined for the entire study population. As the optimal cut-off to define sensitivity to androgen deprivation therapy is not known, the study cohort will be dichotomized into those with 2D:4D ratios above and below the median respectively. The mean percent change from baseline in QOL scores from the collected questionnaires as well as the baseline and mean percent change from baseline in empathy score will be compared between dichotomized subgroups using the Mann-Whitney test.

No adjustment for multiple comparisons will be made for the analysis of the correlative study endpoints.

10. Study Management

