lively _____ lively

not at all _____ totally
bushed _____ bushed

not at all _____ totally
exhausted _____ exhausted

keeping my _____ keeping my
eyes open _____ eyes open
is no effort _____ is a tremendous
at all _____ chore

moving my _____ moving my
body is no _____ body
effort at all _____ is a tremendous
chore

concentrating _____ concentrating
is no effort _____ is a tremendous
at all _____ chore

carrying on _____ carrying on
a conversation _____ a conversation
is no effort _____ is a tremendous
at all _____ chore

I have _____ I have a
absolutely no _____ tremendous
desire to close _____ desire to
my eyes _____ close my eyes

I have _____ I have a
absolutely no _____ tremendous
desire to _____ desire to
lie down _____ lie down

Hot Flash Related Daily Interference Scale (HFRDIS)

Please circle one number to the right of each phrase to describe how much DURING THE PAST WEEK hot flashes have INTERFERED with each aspect of your life. Higher numbers indicate more interference with your life. If you are not experiencing hot flashes or if hot flashes do not interfere with these aspects of your life, please mark zero to the right of each question.

	Do not interfere										Completely interfere
1. Work (work outside the home and housework)	0	1	2	3	4	5	6	7	8	9	10
2. Social activities (time spent with family, friends, etc.)	0	1	2	3	4	5	6	7	8	9	10
3. Leisure activities (time spent relaxing, doing hobbies, etc.)	0	1	2	3	4	5	6	7	8	9	10
4. Sleep	0	1	2	3	4	5	6	7	8	9	10
5. Mood	0	1	2	3	4	5	6	7	8	9	10
6. Concentration	0	1	2	3	4	5	6	7	8	9	10
7. Relations with others	0	1	2	3	4	5	6	7	8	9	10
8. Sexuality	0	1	2	3	4	5	6	7	8	9	10
9. Enjoyment of life	0	1	2	3	4	5	6	7	8	9	10
10. Overall quality of life	0	1	2	3	4	5	6	7	8	9	10

PATIENT HEALTH QUESTIONNAIRE (PHQ-9)

NAME: _____ **DATE:** _____

Over the last 2 weeks, how often have you been bothered by any of the following problems?
(use "✓" to indicate your answer)

	Not at all	Several days	More than half the days	Nearly every day
1. Little interest or pleasure in doing things	0	1	2	3
2. Feeling down, depressed, or hopeless	0	1	2	3
3. Trouble falling or staying asleep, or sleeping too much	0	1	2	3
4. Feeling tired or having little energy	0	1	2	3
5. Poor appetite or overeating	0	1	2	3
6. Feeling bad about yourself—or that you are a failure or have let yourself or your family down	0	1	2	3
7. Trouble concentrating on things, such as reading the newspaper or watching television	0	1	2	3

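### Secondary endpoints are defined as percent change but tested as change, and percent change does not exist for a PHQ-9 or HFRDIS score of zero at baseline

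*Combined protocol and SAP*

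**What the plan says.** The comparative secondary objectives in section 2.2.2 are framed as "To compare the mean percent change from baseline to 12 months and patterns of change over time during participation" in the STAND clinic versus usual care. Sections 3.2.2 and 9.7.2 carry the same metric into the endpoint list: "Mean percent change from baseline to 12 months and patterns of change from baseline with respect to the following". That list runs from glucose, lipids and weight through bone density to the questionnaires, including PHQ-9 and "Hot flash severity as measured by Hot Flash Related Daily Interference Scale".

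The analysis sections use different terms:

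- Section 9.8.1, primary endpoint: "Two-sample t-test will be used to compare the mean percent change from baseline in percentage body fat".
- Section 9.8.2, secondary endpoints: "Two-sample t test will be used to compare the mean change from baseline to 12 months for the secondary endpoints" that meet the normality assumption, with a rank-sum test for non-normal endpoints and ordinal measures.
- Section 9.8.3, finger-length-ratio analysis: "The mean percent change from baseline in QOL scores from the collected questionnaires", compared by Mann-Whitney test.

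Appendix 2 scores the nine PHQ-9 items 0 to 3 and the ten HFRDIS items 0 to 10. The HFRDIS instruction reads: "If you are not experiencing hot flashes or if hot flashes do not interfere with these aspects of your life, please mark zero". Section 4.1 admits men who are only planning ADT as well as men already on it. Section 9.8 imputes endpoints with less than 25% of values missing and excludes those with more than 25% missing. No section says what to do when the baseline score is zero.

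**The concern.** There are two linked defects.

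First, definition and analysis name different quantities. An analyst could follow 9.7.2 or 9.8.2, each with textual support, and reach different answers. Section 9.8.2 makes no multiplicity adjustment for these endpoints, so a choice of metric left open until the data are in weakens what they can show.

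Second, percent change divides by the baseline score. A man with no hot-flash interference at baseline is told to record zero, so his percent change cannot be calculated. This is foreseeable in men enrolled before ADT starts, and they are the men in whom newly emerging ADT toxicity is there to be measured. Baselines just above zero give very large ratios from small movements in score.

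**Working it through.** **Inputs.** Endpoint metric: sections 2.2.2, 3.2.2 and 9.7.2. Analysis metric: sections 9.8.1 to 9.8.3. Score ranges: Appendix 2. Missing-data rule: section 9.8. Sample size and inevaluable rate: section 9.2. The plan states no sample size or power for any secondary endpoint, so there is no figure of its own to reproduce.

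**Step 1. Can the baseline be zero?** Nine PHQ-9 items at 0 give a total of 0. Ten HFRDIS items at 0 give 0, and for a man without hot flashes this is the instructed answer. So yes for both. The line scales (Lee Fatigue, Attentional Function) may also reach zero, but the documents do not give their scoring. Weight, waist, blood pressure, glucose, HbA1c, lipids and bone density cannot be zero.

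**Step 2. What percent change does near zero.** Percent change = 100 × (month 12 − baseline) / baseline. For the same 3-point rise:

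| Baseline | Percent change |
|---|---|
| 0 | undefined |
| 1 | +300% |
| 2 | +150% |
| 5 | +60% |
| 10 | +30% |
| 15 | +20% |

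**Step 3. Can the two metrics disagree?** Illustrative scores for four men:

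| Baseline | Month 12 | Change | Percent change |
|---|---|---|---|
| 1 | 4 | +3 | +300% |
| 2 | 5 | +3 | +150% |
| 10 | 6 | −4 | −40% |
| 12 | 8 | −4 | −33.3% |

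Mean change = (3 + 3 − 4 − 4)/4 = −0.5 points. Mean percent change = (300 + 150 − 40 − 33.3)/4 = +94%. One metric shows improvement, the other worsening.

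**Step 4. How the missing-data rule would act.** Suppose undefined values are treated as missing; the plan does not say. Section 9.8 does not state the denominator either, so take all 80 randomised men.

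- If nothing else is missing, the endpoint is dropped once more than 0.25 × 80 = 20 men have a zero baseline, that is, from 21 men.
- If the 20% inevaluable rate in section 9.2 also applied to the questionnaire (an assumption), 0.20 × 80 = 16 values would already be missing. Five further men with a zero baseline would give 21/80 = 26.25%, and the endpoint would be dropped.
- Below the 25% limit, multiple imputation would fill in a ratio for men who were fully observed and for whom no ratio exists.

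The share of men with a zero baseline is not in the documents, so which branch would apply cannot be determined.

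**The case against.** The strongest reply is that the two defects partly cancel. Section 9.8.2 is the operative analysis text, and read literally it compares absolute change: nothing is divided by baseline and no man becomes undefined. That stands, and it means the certain defect is ambiguity. It does not settle the matter, because three sections define the endpoint the other way, and 9.8.1 and 9.8.3 write percent change where they mean it. Nor does usage elsewhere help: section 1.2.3 describes the bone-density endpoint as mean change, although 9.7.2 lists it under percent change.

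A second reply is that the rank-sum test in 9.8.2 stops very large ratios from dominating. That also stands for defined values. It does not help a man with a zero baseline, who has no percent change to rank, and the Mann-Whitney test in 9.8.3 has the same gap. The repeated-measures and mixed models in 9.8.2 describe patterns over time and do not define the 12-month quantity.

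Third, these are exploratory secondary objectives in a preliminary phase 2 study. That is fair and limits the stakes.

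Two stronger readings are tempting. A reader might infer that the between-arm comparison would be biased. The documents do not show this: losing men because of a baseline score applies one rule to both arms, which changes the population and costs precision but does not by itself favour an arm. A reader might also infer a definite loss of power by borrowing the body-fat effect size from section 9.2. That figure belongs to the primary endpoint, no secondary endpoint is powered, and the missing-data rule would not lead to a simple complete-case analysis.

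**Conclusion.** The point holds as an inconsistency that should be corrected. The metric mismatch touches every secondary endpoint. The zero-baseline problem is established for PHQ-9 and HFRDIS, and section 9.8.3 carries it into the quality-of-life correlative analysis. The consequence is an ambiguous estimand and, if percent change is used, a changed analysis population and lost precision.

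The size cannot be put as a power figure. What can be shown is that the choice of metric can reverse the sign of a mean (−0.5 points against +94% in the example), and that the dropping rule could be reached with anywhere from 5 to 21 zero-baseline men, depending on whether 20% or none of the values are otherwise missing. Both ends of that range assume that undefined values count as missing among 80 men. The primary endpoint and its sample size are not affected.

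**What to change.** Name one metric per endpoint and use the same words in sections 2.2.2, 3.2.2, 9.7.2, 9.8.2 and 9.8.3.

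- **Questionnaire scores:** use absolute change in score, with the 12-month comparison adjusted for baseline score and the stratification factors. Changing the metric is what cures the defect; baseline adjustment is a related improvement, since the t test and rank-sum test now planned at month 12 are unadjusted. Where normality fails, a rank-sum test on absolute change remains defined for every man with both scores.
- **Measures that cannot be zero:** percent change may stay, provided 9.8.2 says so explicitly.
- **Section 9.8.3:** replace percent change in quality-of-life scores with absolute change.

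With absolute change no zero-baseline rule is needed. If percent change is kept for any scale that can be zero, the plan must state how a zero baseline is handled and that it does not count as missing under section 9.8.

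The cost is wording only. Baseline scores and stratification factors are already collected. The change is best made before outcome data are examined by arm.
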